## 4. CLINICAL INVESTIGATION OBJECTIVES

The next stage is for the prototype valve to be tested clinically in humans under research conditions; this will establish if the device reliably opens and closes and is safe to use.

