#### 4.2 Objectives

To assess preliminary safety, effectiveness, reliability, comfort and user acceptability of the valve with adults who have a long-term IDC and the feasibility of undertaking future community-based evaluation.

To do this we will:

- determine if the valve functions reliably i.e. automatically opens to drain urine within acceptable individual bladder volumes with a range of patients;
- determine if the valve functions effectively i.e. allows for the complete bladder emptying (< 100ml post void residual) during rest and daily activities;
- determine if the process of filling and automatic draining is comfortable and acceptable for participants;
- collect preliminary data on the potential for bioburden/biofilm following in human use of the valve;
- assess the feasibility of undertaking a future randomised control trial of the valve.

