#### 4.3 Outcomes

4.3.1 Primary outcomes:

Safety: Reliability

• Valve opening - Proportion of observations of automatic valve opening before bladder capacity (500ml or less) is reached - as measured by bladder scanner (Valve Log)

Safety: Effectiveness

- Bladder emptying proportion of valve voids with residual urine <100ml as measured by bladder scanner (Valve Log)
- Participant report (Valve self-report questionnaire) *Comfort*
- Participant report (Valve self-report questionnaire)

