#### Testing Procedure

With the participant sitting (except when transferring to and lying on the bed for bladder scanning):

- 1. Participant puts on pad with pants to secure it in place
- 2. Record participant's self-reported bladder sensations
- 3. Scan bladder and record volume in Valve Log.
- 4. Research nurse fits the lowest pressure valve according to manufacturer's instructions for use and attach a drainage bag for urine collection. Record Valve Batch/Serial Number in Valve Log.
- 5. Record participant's self-reported bladder sensations in valve log
- 6. Scan bladder and record volume in valve log
- 7. If the valve remains open with urine draining freely, replace with the next level pressure valve (up to 3 valves) until free drainage has ceased and the valve remains closed. Record Valve Batch/Serial Number in Valve Log.

URINARY CATHETER 'FILL AND FLUSH' VALVE:

SAFETY, EFFECTIVENESS, ACCEPTABILITY AND FEASIBILITY TRIAL Protocol Version 3.1 20/08/2019 - IRAS: 245818 - ERGO: 41448

- 8. Participant to lie on bed for hourly bladder scanning (record time and volume in Valve Log) until bladder volume is >400mls or the participant experiences bladder discomfort or the valve automatically opens. Record participant's bladder sensations before each scan and:
  - a. If the volume is >400mls or the participant is experiencing discomfort
    - i. Ask the participant to contract abdominal muscles, press down on abdomen or bear down as if trying to pass urine to increase bladder pressure.
    - ii. If the valve opens, proceed as below (b).
    - iii. If the valve does not open, disconnect the valve, attach a new drainage bag and allow the bladder to drain. Stop the trial for that participant.
  - b. If the valve automatically opens:

Southampton

- i. Record the amount of urine voided
- ii. Scan the bladder for any residual volume
- 9. If the valve has opened with a urine volume of less than 500ml, repeat process 7 & 8 at 1 hourly intervals for 5 hours. If the valve did not open before bladder volume reached 500ml, stop testing at this point.

Participants will be requested to drink a minimum of 500mls of fluids over the first two hours, then a minimum of 150mls per hour for the next 3 hours. They will be given a choice of drinks. After testing has ended for that day, participants will be given a new manual valve and/or drainage bag as per usual use.

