#### Testing Procedure

With the participant sitting (except when transferring to and lying on the bed for bladder scanning):

- 10. Participant puts on pad with pants to secure it in place
- 11. Record participant's self-reported bladder sensations
- 12. Scan bladder and record volume in Valve Log
- **13**. Participant fits the lowest pressure valve according to manufacturer's instructions for use and attach a drainage bag for urine collection.
- 14. Record Valve Batch/Serial Number in Valve Log.
- 15. Record participant's self-reported bladder sensations in valve log
- 16. Scan bladder and record volume in valve log
- 17. If the valve remains open with urine draining freely, replace with the next level pressure valve (up to 3 valves) until free drainage has ceased and the valve remains closed. Record Valve Batch/Serial Number in Valve Log.
- 18. Participant will be asked to stand, walk around and cough at specific intervals as per flowchart in appendix C.

URINARY CATHETER 'FILL AND FLUSH' VALVE:

SAFETY, EFFECTIVENESS, ACCEPTABILITY AND FEASIBILITY TRIAL Protocol Version 3.1 20/08/2019 - IRAS: 245818 - ERGO: 41448

- 19. Record participant's bladder sensations before each scan and:
  - a. If the volume is >400mls or the participant is experiencing discomfort
    - i. Ask the participant to contract abdominal muscles, press down on abdomen or bear down as if trying to pass urine to increase bladder pressure.
    - ii. If the valve opens, proceed as below (b).
    - iii. If the valve does not open, disconnect the valve, attach a new drainage bag and allow the bladder to drain. Stop the trial for that participant.
  - b. If the valve automatically opens:
    - i. Record the amount of urine voided
    - ii. Scan the bladder for any residual volume

As with Day 1, participants will be requested to drink a minimum of 500mls of fluids over the first two hours, then a minimum of 150mls per hour for the next 3 hours. They will be given a choice of drinks. After testing has ended for that day, participants will be given a new manual valve and/or drainage bag as per usual use.

If a participant has to stop testing during Day 1 they will not be eligible for any further testing. All data will be collected by an appropriately trained research nurse (RN).

**Valve Questionnaire**: After all testing is completed; participants will complete a Valve Questionnaire to assess the valve for comfort.

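### The trial's stated purpose includes valve closing, but no outcome or planned count scores it, and the visible text does not classify a participant in whom all three variants drain freely

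*Protocol*

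**What the plan says.** Section 4 (Clinical Investigation Objectives) gives the purpose of the human test: "this will establish if the device reliably opens and closes and is safe to use". Both halves of the valve's action are promised.

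Section 4.2 narrows reliability to opening: "determine if the valve functions reliably i.e. automatically opens to drain urine within acceptable individual bladder volumes with a range of patients". Section 4.3.1 does the same for the primary reliability outcome: "Proportion of observations of automatic valve opening before bladder capacity (500ml or less) is reached". The other scanner-based primary outcome, effectiveness, is the "proportion of valve voids with residual urine <100ml as measured by bladder scanner (Valve Log").

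In Section 5.6.1, testing starts with the lowest-pressure variant. Step 7 then says: "If the valve remains open with urine draining freely, replace with the next level pressure valve (up to 3 valves". The valve's batch or serial number goes into the Valve Log. Step 9 applies when a valve has opened at under 500 ml, and tells staff to "repeat process 7 & 8 at 1 hourly intervals for 5 hours". In Section 5.6.2, step 17 repeats the swap rule for Day 2, "until free drainage has ceased and the valve remains closed".

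The rules in the testing steps for ending a participant's testing (steps 8a, 9 and 19a) are all conditional on the valve not opening. In Table 2 of Section 6.1.1, failure to open is the only valve malfunction listed. Section 5.9.1 plans to summarise bladder volume at opening and residual volume at closing, by activity.

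**The concern.** The device is meant to let the bladder fill and then empty. A valve that stays open gives ordinary free drainage, the arrangement that the background section argues the device should improve on. Closing is therefore central to whether the valve works, and the bench work in Section 3.5 was reported in terms of both opening and closing.

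As the outcomes are written, a valve that does not close is exchanged and scored nowhere. Two things follow. The reliability proportion describes only valves that passed the closing check. And if the third variant also drains freely, the visible procedure has no next step and no classification. Depending on how the team handles that, the worst closing result could be left out of the primary outcomes or counted in their favour.

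**Working it through.** The protocol gives no power, precision or target proportion for n = 16, so there is no stated figure to reproduce. The check has two parts.

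**1. Where could a failure to close be scored?**

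| Place in protocol | What it captures | Scores closing? |
|---|---|---|
| 4, purpose | opening and closing | promised |
| 4.2, reliability objective | opening | no |
| 4.3.1, reliability | opening at 500 ml or less | no |
| 4.3.1, effectiveness | residual under 100 ml per void | no |
| 5.6.1 and 5.6.2, ending of testing | not opening | no |
| 5.9.1, analysis | volumes at opening and at closing | no count of swaps or non-closures |
| 6.1.1, Table 2 | not opening | no |

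The 5.9.1 entry comes closest. It describes the residual for valves that did close, and does not count those that did not.

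**2. A participant in whom all three variants drain freely**

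Urine keeps draining, so the bladder need not fill to the 400 ml trigger in step 8a or the 500 ml limit in step 9. Two readings of the outcomes are open:

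- Reading A: no automatic opening is observed, so the participant contributes no observations.
- Reading B: the valve is open below 500 ml and the residual is below 100 ml, so the participant counts as a success on both scanner-based outcomes.

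Let k be the number of such participants among 16, and let v be the number of observations per contributing participant, all successful and equal across participants. Both k and v are assumptions.

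- Reading A: opening proportion = (16 − k)v / (16 − k)v = 100%.
- Reading B: opening proportion = 16v / 16v = 100%.
- Participants with a closing variant = (16 − k)/16.

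For k = 3, the last line gives 13/16 = 81%, against 100% under either reading. Across a range of k, with exact (Clopper-Pearson) 95% intervals:

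| k | With a closing variant | 95% interval |
|---|---|---|
| 0 | 16/16 = 100% | 79 to 100% |
| 1 | 15/16 = 94% | 70 to 99.8% |
| 2 | 14/16 = 88% | 62 to 98% |
| 4 | 12/16 = 75% | 48 to 93% |
| 8 | 8/16 = 50% | 25 to 75% |

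The opening proportion is 100% in every row. The protocol's unit for that outcome is observations and the column above counts participants, so the two are set side by side and are not the same measure.

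Whether the case would arise at all depends on an unknown rate q. The chance of at least one such participant is 1 − (1 − q)^16, which is 0.560 for q = 5%, 0.815 for q = 10% and 0.972 for q = 20%.

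**The case against.** The strongest reply is that the data largely exist. Every day starts with the lowest variant, free drainage is the only stated reason to swap, and each serial number is logged, so most swaps could be counted afterwards. That stands, and a reader who inferred that the trial cannot show closing would be going too far. The reply is incomplete in two respects. A failure of the third variant produces no fourth serial number, so its serial trail looks the same as that of a participant whose high-pressure valve worked. Serial numbers alone also do not separate a swap at first fitting from a failure to re-close later.

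Second, moving up a variant is partly selection. Section 3.2 says bladders work at different pressures and makes finding the suitable variant an aim. A low-pressure valve that drains freely need not be faulty. This stands, and it is why the two kinds of swap should be counted separately.

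Third, a valve that opens in step 8 and then fails to re-close does not vanish from the results: its voided volume and residual are recorded under step 8b before step 7 is repeated. This also stands. What goes uncounted is the failure to re-close.

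Fourth, the flow charts in Appendices B and C and the Valve Log form are not visible and may contain a branch for a third freely draining variant. Such a participant might also be treated as not having completed the protocol successfully under Section 6.3, although that term is not defined. A reader might infer that this participant records no failure; the documents support only that the visible text leaves the classification open.

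A reader might also suspect that starting bladder volume differs between manual-valve and free-drainage users and so drives which variant is kept. The protocol gives no starting volumes by group, so that is not claimed here.

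**Conclusion.** The point holds as a gap between purpose and measurement. Section 4 promises evidence on opening and closing, the primary outcomes cover opening and emptying, and the swap rule makes the reliability proportion conditional on a variant that closes. The visible text also does not say how a participant with no closing variant enters the primary outcomes.

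The size cannot be known from the protocol. The contrast of 100% with 81% rests on an assumed 3 of 16 participants, on all other observations succeeding, and on either of the two readings above. If every participant has a variant that closes and re-closes, the gap has no numerical effect. The change should be made, because the primary outcome itself is fixed in the protocol and omits half of the stated purpose.

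**What to change.** This is a change to measurement and scoring only; it alters no procedure for managing the participant.

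- In Section 4.3.1, add a closing component to the reliability outcome, reported per participant and per variant.
- In the Valve Log, record the time, reason and bladder volume at each swap. The scans in steps 3 and 6 (steps 12 and 16 on Day 2) surround only the first fitting, so they cannot serve to classify later valves. The 100 ml residual limit was set for emptying and should not be reused as a test of closing.
- Count swaps at first fitting, which are partly variant selection, separately from failures to re-close after a void.
- State that a participant in whom no variant stays closed counts as a reliability failure and is left out of the residual-volume proportion, since continuous drainage yields no separate void to assess.
- Report the variant retained for each participant, which also serves the aim in Section 3.2.
- If Appendix B or C already has a branch for a third freely draining variant, refer to it in the outcome definition.

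The cost is revised outcome wording, a few log entries and a bladder volume at each swap. Reported reliability may be lower than under the present definition.

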## 5.6.2 Trial Procedures Day 2 - Ambulatory testing

#### Pre-testing

- Confirm no changes to eligibility, answer any questions and ask participant to re-confirm consent (recorded on Day 2 Case report form).
- First drink (250mls) provided.
- Take baseline observations and record on Day 2 Case report form: blood pressure, temperature, pulse and respiratory rate.
- Participant completes Quality of Life tools: EQ-5D-5L and Long-term Catheter Quality of Life Tool.

#### Testing Procedure

With the participant sitting (except when transferring to and lying on the bed for bladder scanning):

- 10. Participant puts on pad with pants to secure it in place
- 11. Record participant's self-reported bladder sensations
- 12. Scan bladder and record volume in Valve Log
- **13**. Participant fits the lowest pressure valve according to manufacturer's instructions for use and attach a drainage bag for urine collection.
- 14. Record Valve Batch/Serial Number in Valve Log.
- 15. Record participant's self-reported bladder sensations in valve log
- 16. Scan bladder and record volume in valve log
- 17. If the valve remains open with urine draining freely, replace with the next level pressure valve (up to 3 valves) until free drainage has ceased and the valve remains closed. Record Valve Batch/Serial Number in Valve Log.
- 18. Participant will be asked to stand, walk around and cough at specific intervals as per flowchart in appendix C.

URINARY CATHETER 'FILL AND FLUSH' VALVE:

SAFETY, EFFECTIVENESS, ACCEPTABILITY AND FEASIBILITY TRIAL Protocol Version 3.1 20/08/2019 - IRAS: 245818 - ERGO: 41448

- 19. Record participant's bladder sensations before each scan and:
  - a. If the volume is >400mls or the participant is experiencing discomfort
    - i. Ask the participant to contract abdominal muscles, press down on abdomen or bear down as if trying to pass urine to increase bladder pressure.
    - ii. If the valve opens, proceed as below (b).
    - iii. If the valve does not open, disconnect the valve, attach a new drainage bag and allow the bladder to drain. Stop the trial for that participant.
  - b. If the valve automatically opens:
    - i. Record the amount of urine voided
    - ii. Scan the bladder for any residual volume

As with Day 1, participants will be requested to drink a minimum of 500mls of fluids over the first two hours, then a minimum of 150mls per hour for the next 3 hours. They will be given a choice of drinks. After testing has ended for that day, participants will be given a new manual valve and/or drainage bag as per usual use.

If a participant has to stop testing during Day 1 they will not be eligible for any further testing. All data will be collected by an appropriately trained research nurse (RN).

**Valve Questionnaire**: After all testing is completed; participants will complete a Valve Questionnaire to assess the valve for comfort.

**Microbiological Testing:** Used valves will be collected and placed in individual, labelled, sealed plastic bags. These will be transported to the ACDP Containment Level 2 microbiology laboratory in the Life Sciences Building, Highfield Campus, University of Southampton. Valves will be packaged as UN 3373 Biological Category B specimens for transportation. The sealed bags will be placed in secondary packaging with absorbent tissue. This will be sealed and labelled UN 3373. Samples will then be transferred to the laboratory and only opened within the Containment 2 facility.

If there is a delay between collection of used valves and transportation to the laboratory, the sealed bags will be stored in a refrigerator until collection. This will prevent additional growth of any bacteria which may be present.

All laboratory staff will be adequately trained in GCP and according to all applicable local policies and procedures.

## 5.7 Withdrawal:

Participants will be able to withdraw from the study at any point without giving a reason. Withdrawal will be recorded in the Case Report Form.

#### 5.8 IDC Management after End of the study:

Once the participant has completed the study s/he will be advised to revert to his usual method of IDC management.

## 5.9 Data Analysis:

5.9.1 Clinical

Descriptive statistics will be used to summarise

- Demographics of participants
  - Total number and percentage of men and women will be reported
  - Total number and percentage from each age groups will be reported
- Bladder volume when the valve opened and residual bladder volume when the valve closed while undertaking different activities
  - The range and mean average of the volume of urine in the bladder at each valve opening for each activity will be reported.
- Questionnaire findings (for each occasion the questionnaire is completed)
  - For binary questions (yes/no), the total number and percentage of each answer will be recorded
  - For scale response questions, the total and percentage number of participants answering each response (e.g. Very comfortable, Quite comfortable, neither comfortable or uncomfortable, Quite uncomfortable, Very uncomfortable) will be reported.

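### Section 5.9.1 summarises bladder volume only at valve openings, so its mean and upper range are biased low: negligibly for a valve that opens well below 400 ml, by tens of millilitres for a stiff one

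*Protocol*

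**What the plan says.** Section 5.9.1 fixes the statistic for opening volume: "The range and mean average of the volume of urine in the bladder at each valve opening for each activity will be reported". It lists no count of fills that end without an opening, and it does not list the section 4.3.1 reliability proportion among its summaries.

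Section 5.6.1 (Day 1) sets how a fill can end. Step 8 begins: "Participant to lie on bed for hourly bladder scanning". The action rule is triggered thus: "If the volume is >400mls or the participant is experiencing discomfort". The participant is first asked to strain. A valve that then opens is handled like any other opening, with voided and residual volumes recorded. Otherwise: "If the valve does not open, disconnect the valve, attach a new drainage bag and allow the bladder to drain", and testing stops for that participant. Section 5.6.2 (Day 2, step 19a) repeats the rule and bars anyone stopped on Day 1 from further testing. Step 9 of section 5.6.1 adds a different limit: "If the valve did not open before bladder volume reached 500ml, stop testing at this point".

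The related objective in section 4.2 is to "determine if the valve functions reliably i.e. automatically opens to drain urine within acceptable individual bladder volumes with a range of patients". Section 4.3.1 measures this as the proportion of observations with automatic opening at 500 ml or less.

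**The concern.** When a valve is disconnected unopened, its opening volume is known only to exceed the last scanned volume. It is right-censored, and the censoring is caused by the quantity being measured. A summary taken at openings answers a conditional question: at what volume did the valve open, given that it opened before removal? High-threshold fills are selectively absent, which lowers the mean. The top of the range is set by the removal rule and the scan interval as well as by the valve.

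The selection compounds across days. A participant whose valve fails on Day 1 contributes no value for the failed fill and none on Day 2, while a participant whose valve works can contribute repeated openings on both days. Because section 5.9.1 reports by activity, the ambulatory figures come only from people who were not stopped on Day 1.

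At stake is how well this summary separates valves that open early from valves that open late. Section 3.2 gives learning which variant works, and in what circumstances, as an aim of the study.

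**Working it through.** The protocol states no mean, SD or expected share of openings, so there is no figure of its own to reproduce. The direction follows from the rules above. The size was illustrated in two ways.

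**Inputs from the protocol:** removal trigger at a scan above 400 ml; hourly scans; straining before removal; 500 ml in the primary outcome.

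**Assumptions, not in the protocol:** opening volume normal, with true mean 300 to 500 ml and SD 80 to 120 ml; filling at 100, 150 or 250 ml/h (SD 20% of the rate); starting volume uniform on 0 to 100 ml; straining opens 0% or 50% of valves still closed, entered at the scanned volume. Removal for discomfort at lower volumes was not modelled.

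**1. Sharp cut at c = 400 ml.** The mean among openings is μ − SD × φ(a)/Φ(a), with a = (c − μ)/SD. For μ = 500 and SD = 80, a = −1.25, φ = 0.1826 and Φ = 0.1056, so the mean is 500 − 80 × 1.729 = 362 ml.

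| True mean (SD 80) | Share opening | Mean among openings | Bias |
|---|---|---|---|
| 300 | 89% | 284 | −16 |
| 400 | 50% | 336 | −64 |
| 450 | 27% | 351 | −99 |
| 500 | 11% | 362 | −138 |

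Valves whose true means differ by 100 ml (400 and 500) are reported 26 ml apart (336 and 362).

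Equivalently, with s the share unopened and z the (1 − s) quantile, the bias is −SD × φ(z)/(1 − s). With SD 100 and s = 10%, 20%, 30% and 50%, the mean is understated by 19, 35, 50 and 80 ml.

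**2. Hourly scans.** A sharp cut overstates the effect, because a valve can open above 400 ml between scans. Simulating 400,000 fills per scenario, with removal at the first hourly scan above 400 ml, gives the following at 100 / 150 / 250 ml/h (biases come from unrounded means):

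| True mean, SD | Removed unopened, no strain openings | Bias (ml), no strain openings | Bias (ml), 50% strain openings |
|---|---|---|---|
| 300, 80 | 4 / 3 / 1% | −7 / −5 / −2 | −4 / −3 / −1 |
| 400, 80 | 28 / 21 / 10% | −35 / −26 / −11 | −23 / −17 / −8 |
| 500, 80 | 72 / 61 / 34% | −90 / −67 / −31 | −71 / −55 / −28 |
| 500, 120 | 66 / 58 / 37% | −124 / −103 / −60 | −90 / −76 / −46 |

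The bias is downward in every scenario and grows with the true opening volume.

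**3. Denominator of the reliability proportion.** For the 500 ml, SD 80 valve without strain openings, automatic opening at 500 ml or less occurs in 28% to 44% of all fills. Among openings only, the figure is 66% to 99%. Section 4.3.1 refers to observations without saying whether an unopened fill is one.

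**The case against.** A reader might infer that the summary makes a stiff valve look acceptable. The protocol does not support that. The section 4.2 objective is a yes/no question for each fill, and it is answered by the section 4.3.1 proportion; the mean in section 5.9.1 only describes. Failures would also be visible elsewhere. Each unopened valve stops that participant, valve non-opening is a recorded solicited event (section 6.1.1), and the trial stops if none of the first four participants completes (section 6.3). Assuming four independent fills per participant (not in the protocol), per-fill non-opening of 10%, 20%, 30% or 50% would stop 1 − 0.9⁴ = 34%, 1 − 0.8⁴ = 59%, 1 − 0.7⁴ = 76% or 1 − 0.5⁴ = 94% of participants. A large bias would therefore come with many visible stops.

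Other limits also stand. Section 5.9.1 is silent on unopened fills, which is not the same as excluding them from the report, and a separate analysis plan might count them. Opening volume is not the only continuous measure, since residual volume is summarised too. No section says that the mean will decide the choice of variant, and section 5.9.1 reports by activity rather than by variant. Straining and hourly scans mean that 400 ml is not a sharp ceiling.

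None of this changes the stated statistic. A mean over openings omits the unopened fills whatever is reported elsewhere, and the reliability proportion is a safeguard only if all fills are in its denominator.

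**Conclusion.** The point holds for the opening-volume summary alone. Its mean and upper range are conditional on opening and biased low. Under the hourly-scan assumptions with SD 80 ml, the bias is at most 7 ml for a true mean of 300 ml. For a true mean of 500 ml it is 31 to 90 ml without strain openings and 28 to 71 ml with half of the remaining valves opened by straining. At SD 120 ml it reaches 124 ml. These sizes are illustrations, because the protocol gives no opening-volume distribution; the downward direction follows from the removal rule. The section 4.3.1 proportion is not affected if it counts all fills. The change is worth making because the statistic is fixed in the protocol and the remedy is small.

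**What to change.** In section 5.9.1, for each activity and valve variant:

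- Report the proportion of all fills that opened automatically by set volumes, including the 500 ml of the primary outcome. Count valves removed unopened, whether for volume or discomfort, as not opened.
- If the mean and range are kept, label them as among openings only. Print beside them the number of unopened fills and their last scanned volumes.
- Show openings after straining separately from automatic ones.

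In section 4.3.1, state that the denominator of the reliability proportion is all fills.

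A Kaplan-Meier median over bladder volume is optional. Repeated fills within 16 participants, hourly interval-censoring and possibly informative removal for discomfort all weaken it.

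The investigators must reconcile the 400 ml limit (step 8) with the 500 ml limit (step 9 and section 4.3.1); no view is taken here on either.

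The cost is a few lines of analysis text. Scan volumes and valve serial numbers are already in the Valve Log. The table becomes slightly longer, and the opening-volume picture may be less favourable.
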